#### Risk associated with biopsy of ethmoid tissue at end of treatment course

The main risk associated with biopsy of ethmoid tissue performed in clinic is discomfort and bleeding at biopsy site. These risks will be minimized by application of topical anesthetics prior to the biopsy and vasoconstrictor (afrin) after the biopsy is performed.

#### Risk associated with confidentiality

The research data may need to be reviewed by the IRB and/or sponsor. This may be necessary for internal audits or for review of the raw data prior to publication. In order to maintain confidentiality, patients will be assigned a study ID number which will be used to associate the blood samples and tissue biopsies to the patient. A data sheet correlating the patient's names and date of birth with their study number will be made and stored electronically on [name] institutionally-proved computer in a password protected encrypted file. In addition, electronic data sheets will be stored on [name] institutionally-proved computer in a password protected encrypted file to minimize this risk of breach of confidentiality.

#### **Patient Withdrawal from Study**

Patients are free to withdraw from the study at any point in the study. In addition, patients can be withdrawn from the study by investigators if patients do not fulfill inclusion criteria, meet exclusion criteria, develop any complications from administered medications, and/or develop recurrent nasal polyps requiring medical or surgical intervention.

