This study is a **randomized control trial**, in which patients and treating physicians will be blinded, designed to test whether itraconazole after surgery in fungal sensitive, fungal culture positive CRSwNP patients will have decreased rates of nasal polyp recurrence as compared to placebo treated patients (Figure 1). **The study population will come from the rhinology practice of the Department of Otorhinolaryngology where 3 rhinologists practice** (Drs. [name], [name], and [name]) as well as the rhinology practices at UTSW and UTSA. Among the 3 rhinologists of UT Houston, approximately 150 sinus surgeries are scheduled annually involving CRSwNP. Definitions of CRSwNP are based on the criteria outlined by The Rhinosinusitis Initiative[6]. Inclusion and exclusion criteria are listed in Table 1. Up to 500 CRSwNP patients undergoing a medically-indicated sinus surgery over 3-4 years will be screened and recruited to undergo peripheral blood draw that will be used in an *in vitro* ELISpot assay to identify those that are fungal sensitive. Blood from UTSA and UTSW will be shipped to UT Houston for processing. We anticipate that 80% of those screened patients will meet inclusion criteria allowing us to enroll about 400 CRSwNP patients undergoing sinus surgery. After surgery, patients will be randomized into 1 of 2 groups (1:1 ratio, stratified by presence of asthma): 1) oral itraconazole (200 mg q12 hrs) or 2) placebo for 24 weeks. Patients will be evaluated in the clinic on post-treatment weeks 2 ( $\pm$  1 week), 6 ( $\pm$  2 weeks), 12 ( $\pm$  2 weeks), and 24 ( $\pm$  3 weeks) as per the typical post-operative management protocol (Figure 2). Patients will be clinically followed for an additional 24 weeks post-treatment for recurrent nasal polyps. Therefore, patients will be followed for a total of 48 weeks after sinus surgery or until recurrent nasal polyps requiring treatment are noted.

It is current standard practice for all CRS patients to complete validated health assessment questionnaires for CRS (SNOT-22) and undergo recorded nasal endoscopic exams at each clinic visit. All medications and any treatment side effects will be recorded at each clinic visit.

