Blood will be drawn on the day of surgery for the ELISpot assay and for a baseline hepatic function. Medication compliance will be assessed by counting remaining pills at each follow-up visit. A small amount of diseased ethmoid tissue at time of surgery and post-treatment (either at time of recurrent nasal polyps or completion of 24 week treatment) will be obtained and analyzed by microarray for subjects enrolled at the UT Houston site. Sinus secretions will be sampled from the ethmoid sinus cavity at time of surgery and at clinic visit when study medication is stopped for subjects enrolled at the UT Houston site.

[figure not shown]
**Study endpoints:** The primary efficacy endpoint is recurrence of nasal polyps requiring medical intervention over 48 weeks post-surgery. Nasal endoscopy will evaluate for recurrent nasal polyps and will be scored using a nasal endoscopy scoring system. Intervention for recurrent nasal polyps with prednisone will be determined clinically by the blinded treating physician. The secondary endpoints will be validated health assessment scores (SNOT-22) for CRS, nasal endoscopy scores, and qualitative and quantitative fungal cultures.

The safety endpoints will include possible adverse events associated with itraconazole (e.g., EKG changes shortness of breath, and anaphylactic reactions to itraconazole or intolerable side effects requiring the patient to stop study medication).

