**Monitored post-operative by nasal endoscopy, subjective symptoms, adverse reactions, and collection of ethmoid tissue**

As noted in Figure 2, patients will be seen for routine post-operative clinic visits as per typical post-operative standardized care. During these clinic visits, patients routinely undergo review of sinus symptoms, health, medication, and nasal endoscopy and complete health assessment questionnaires. In addition, patients will be asked about any specific adverse events commonly associated with itraconazole as noted above.

For those noted to have recurrent nasal polyps requiring medical intervention, a small biopsy of ethmoid diseased sinusal polyp mucosa will be obtained and stored at -80C for microarray analysis.

For those without recurrent nasal polyps, a small biopsy of ethmoid sinusal mucosa will be obtained and stored at -80C for microarray analysis at post-treatment week 24.

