**Risk associated with itraconazole, an oral anti-fungal**

Itraconazole is an oral anti-fungal introduced in 1984 that has been utilized in a number of different reported retrospective studies and clinical trials. The FDA has a boxed warning for cardiac effects and drug interactions. From these studies, no serious adverse events were reported with approximately 10% reporting side effects with an incidence no higher than 11% (nausea). Patients experiencing any intolerable side effects may choose to withdraw from the study. Itraconazole is metabolized in the liver and as such patients will be screened for a history of impaired hepatic function.

Patients will be excluded for concomitant use of drugs considered to be contraindicated with the use of Itraconazole. These drugs are:

- a. quinidine (such as Cardioquin® , Quinaglute® , Quinidex® ) .
- b. dofetilide (such as Tikosyn™) .
- c. cisapride (such as Propulsid® ) .
- d. pimozide (such as Orap® ) .
- e. methadone (such as Dolophine® ) .
- f. disopyramide (such as Norpace® ) .
- g. dronedarone (such as Multaq® ) .
- h. ranolazine (such as Ranexa® ) .
- i. lovastatin (such as Mevacor® , Advicor® , Altocor™)
- j. simvastatin (such as Zocor® )
- k. triazolam (such as Halcion® )

- I. midazolam (such as Versed®) ·
- m. lurasidone (such as Latuda®) ·
- n. nisoldipine (such as Sular®) ·
- o. felodipine (such as Plendil®) ·
- p. ergot alkaloids (such as Migranal®, Ergonovine, Cafergot®, Methergine®) ·
- q. eplerenone (such as Inspira®) ·
- r. irinotecan (such as Camptosar®) ·
- s. colchicine (such as Colcrys™) [if you also have pre-existing kidney or liver impairment]

Patients will be screened at each study visit for impaired liver function by asking about symptoms of nausea, vomiting, abdominal pain, swelling of the feet or yellowing of the eyes and skin. Baseline hepatic function will be determined via bloodwork and those with elevated levels will be excluded from the study. Cardiac changes will be monitored at each study clinic visit by asking questions specifically about history of orthopnea, paroxysmal nocturnal dyspnea, dyspnea on exertion with routine activities and changes in exercise tolerance over the treatment course. EKG changes from baseline as defined below will be stopped on study medication.

- 1) Use a QTc interval of 470 ms (males) and 480 ms (females) as the upper limit of normal.
- 2) Discontinue the medication if the QTc > 500 or if it increases by more than 60 ms from baseline.

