- 3) Federicia formula to calculate the Qtc ( $QTc = QT/(RR)^{1/3}$ ) will be used
- 4) Patients that have a QTc > 470 (male) or > 480 (female) but still < 500, ECG recheck after 4 half-lives (10 days). If the QTc meets any of the exclusion criteria then they are excluded from the study. If the Qtc remains acceptable then recheck at 1 month.

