#### **Data and Safety Monitoring**

A Data Safety Monitoring Board will be established and chaired by [name] (Pediatric Allergist). In addition, other members of the Board will consist of [name] (anesthesiologist and member of IRB) and [name] (Director of the Laboratory of Mycology Research). This committee will meet at the beginning of the study and regularly throughout the duration of the clinical trial to oversee the progress of the trial including any adverse events and to ensure patient safety. Any adverse events occurring during the duration of the study will be recorded on the patient's data sheets. If the adverse event such as bleeding is controlled, the subject will be offered the opportunity to continue or discontinue involvement in the study. They will be promptly reported to the CPHS according to the established protocol. Again, subjects may opt to discontinue involvement of the study at any time. The CPHS will be updated to the progress of the study per established protocol.

If at any time >5% of the study population experiences a serious adverse reaction, the study will be stopped until the Data Safety Monitoring Board has time to convene and discuss the event and safety of the trial.

Given minimal adverse events with study drug and additional documentation from other larger clinical trials using oral itraconazole, the protocol was changed and approved such that hepatic function only needed to be checked at the beginning of the trial and monitored via symptoms and cardiac function was monitored with EKG and symptoms. As such, the DSMB with outside expertise on possible itraconazole adverse events seemed unnecessary. In its place, Drs. [name], [name] and [name] meet monthly to review all active trials and research projects associated with the rhinology group. At this meeting, any adverse events or irregularities with the trial will be reviewed and documented.

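### Investigators may withdraw randomised patients from the study for any medication complication, and the plan does not say that such patients are followed for recurrence or analysed by assigned arm.

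*Combined protocol and SAP*

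**What the plan says.** Study Design (Aim 1) sets the general rule: "patients will be followed for a total of 48 weeks after sinus surgery or until recurrent nasal polyps requiring treatment are noted". It splits this period into 24 weeks on medication and 24 weeks afterwards, so off-treatment follow-up is planned for patients who complete the course.

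Patient Withdrawal from Study adds another way out. Besides the patient's own right to leave, "patients can be withdrawn from the study by investigators if patients do not fulfill inclusion criteria, meet exclusion criteria, develop any complications from administered medications". The sentence sets no severity threshold and does not separate stopping drug from leaving the study. The phrase about administered medications covers itraconazole and placebo, and could also cover the prednisone course that both arms receive. Recurrence needing intervention is a further reason in the same sentence, but the primary event has then already been recorded.

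The section on itraconazole risk uses two wordings for QTc changes. The list is introduced with "EKG changes from baseline as defined below will be stopped on study medication", while its item 4 says "If the QTc meets any of the exclusion criteria then they are excluded from the study".

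Data and Safety Monitoring says that after a controlled adverse event "the subject will be offered the opportunity to continue or discontinue involvement in the study". It does not mention stopping drug while staying in follow-up.

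Statistics, Power analysis gives estimation of an unbiased treatment effect as the goal. It names no analysis set and no handling of missing outcomes. Dropout appears there only as a reduction in sample size.

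**The concern.** The primary endpoint is recurrence needing medical intervention over 48 weeks. A patient who leaves the study at, say, week 8 because of a drug complication has an unknown outcome from then on unless someone keeps recording it. Complications of the study capsules may be more frequent on itraconazole than on placebo, so such losses may be unequal by arm. If those who leave also differ in their risk of recurrence, a comparison of the remaining patients is no longer a comparison of the randomised groups.

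Outcomes that were never collected cannot be recovered at analysis. That is why the follow-up rule has to be settled in advance, even if the eventual bias proves small.

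**Working it through.** **1. The plan's own figures.** Study Design expects about 400 eligible patients from 500 screened (500 × 0.80). The power section then gives:

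- 400 × (1 − 0.15) = 340, as stated for final analyses
- 120 × (1 − 0.15) = 102, as stated for the low-recruitment case

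Both reproduce exactly. Dropout is used only to shrink N. This is consistent with leaving dropouts out of the analysis, but the plan does not say so.

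**2. The passages side by side.**

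| Section | Situation | What happens | Recurrence follow-up afterwards |
|---|---|---|---|
| Study Design | Patients in general | 48 weeks, or until recurrence | Stated |
| Itraconazole risk, introduction to QTc list | QTc change | Study medication stopped | Not stated |
| Itraconazole risk, QTc item 4 | QTc change at recheck | Excluded from the study | Not stated |
| Patient Withdrawal from Study | Any medication complication | May be withdrawn from the study | Not stated |

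The two QTc wordings may mean the same thing, but they read differently and must be reconciled.

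**3. What deletion of leavers could do (illustration).**

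Inputs:
- True recurrence 50% in both arms (the placebo rate in Table 2, with no treatment effect).
- n = 200 per arm (400/2) or 60 per arm (120/2) before exits.
- w = share of the itraconazole arm that exits: 5%, 11% or 15%. All are assumptions. The 11% is the document's nausea incidence and the 15% its total dropout; neither is a known drug-related exit rate.
- r = recurrence risk among leavers: 30%, 50% or 70%, assumed.
- All exits on itraconazole, leavers deleted.

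Formulas:
- Apparent itraconazole rate: p′ = (0.5 − w·r)/(1 − w)
- Shift: 0.5 − p′
- SE = √[0.25/n + p′(1 − p′)/(n(1 − w))]
- Type I error: Φ(−1.96 + z) + Φ(−1.96 − z), with z = shift/SE

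Worked case, w = 0.15, r = 0.70, n = 200:
- p′ = (0.5 − 0.105)/0.85 = 0.4647, so the shift is 3.53 points
- SE = 0.0521 and z = 0.0353/0.0521 = 0.678
- Type I error = 10.4%

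With r = 0.30 the shift has the same size in the opposite direction.

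| Exits on itraconazole | Shift, r = 30% or 70% (points, either direction) | Type I error, 200 per arm | Type I error, 60 per arm |
|---|---|---|---|
| 5% | 1.05 | 5.50% | 5.15% |
| 11% | 2.47 | 7.68% | 5.80% |
| 15% | 3.53 | 10.40% | 6.59% |

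Softer cases at 200 per arm:
- Half as many exit (2.5%, 5.5%, 7.5%): shift 0.51, 1.16 or 1.62 points; type I error 5.12%, 5.61% or 6.17%.
- Placebo patients exit at half the itraconazole rate (7.5% against 15%): shift 1.91 points; type I error 6.49%.
- Leavers at average risk (r = 50%): shift 0, type I error 5.0% at every exit rate.

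**The case against.** The case on the other side has several parts.

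- **Off-treatment follow-up is already planned.** Study Design follows patients for 24 weeks after treatment, so the plan does distinguish being off drug from being out of the study. This stands, and it narrows the gap to patients who stop early or are withdrawn. In addition, "patients will be seen for routine post-operative clinic visits as per typical post-operative standardized care", so some outcomes may be recorded anyway; the plan does not say that they are collected or used after withdrawal.
- **Withdrawal is discretionary, and patients and treating physicians are blinded.** An investigator cannot knowingly remove patients to favour an arm. This stands. Blinding does not, however, equalise the complications themselves.
- **Few exits may occur.** Data and Safety Monitoring describes adverse events with study drug as minimal, and exits due to prednisone need not differ by arm. Both points weaken the larger scenarios.
- **This is a pilot.** But its stated goal is estimation without bias, which informative loss threatens at any sample size.

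Three stronger readings are tempting, and the documents do not support them.

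- A reader might infer that withdrawn patients will be excluded from the analysis. The plan is silent; subtracting dropout only suggests it.
- A reader might see a contradiction between the safety endpoint ("intolerable side effects requiring the patient to stop study medication") and the statement "Patients experiencing any intolerable side effects may choose to withdraw from the study". The first defines an endpoint and the second restates a patient's right; both can be true.
- A reader might take 10.4% as the expected error rate. It needs the whole 15% dropout to fall on itraconazole and leavers to be 20 points from average risk.

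**Conclusion.** The point holds as a gap in the rules, not as a demonstrated bias. The plan permits removal from the study for a medication complication of any severity, and it neither keeps such patients in recurrence follow-up nor states analysis by assigned arm. The QTc wordings need reconciling.

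Under the assumed scenarios the effect runs from nothing to a shift of about 3.5 points in either direction, and the type I error from 5% to about 10% at 200 per arm (at most 6.6% at 60 per arm). The documents supply neither a drug-related exit rate nor the recurrence risk of leavers, so these figures show sensitivity and do not forecast. The change is a cheap improvement and worth making before data are seen.

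**What to change.** Leave every rule for stopping study drug unchanged.

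1. Reconcile the QTc wordings in the itraconazole risk section and the Patient Withdrawal section with the 48-week follow-up in Study Design. State that stopping study drug is not study withdrawal, and that such patients remain in recurrence follow-up to week 48 unless they withdraw consent.
2. In Statistics, state that all randomised patients are analysed by assigned arm, stratified by asthma, using partial follow-up (for example, time to recurrence). Add a sensitivity analysis in which patients lost early have higher or lower recurrence risk than those retained.

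The cost is a few sentences of wording, plus contact or visits to week 48 for patients off drug; Study Design gives dated visits only to week 24. Keeping patients who have stopped drug in their assigned arm also dilutes the on-drug contrast. That is the usual price of comparing the groups as randomised.

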#### **Data and Safety Monitoring**

A Data Safety Monitoring Board will be established and chaired by [name] (Pediatric Allergist). In addition, other members of the Board will consist of [name] (anesthesiologist and member of IRB) and [name] (Director of the Laboratory of Mycology Research). This committee will meet at the beginning of the study and regularly throughout the duration of the clinical trial to oversee the progress of the trial including any adverse events and to ensure patient safety. Any adverse events occurring during the duration of the study will be recorded on the patient's data sheets. If the adverse event such as bleeding is controlled, the subject will be offered the opportunity to continue or discontinue involvement in the study. They will be promptly reported to the CPHS according to the established protocol. Again, subjects may opt to discontinue involvement of the study at any time. The CPHS will be updated to the progress of the study per established protocol.

If at any time >5% of the study population experiences a serious adverse reaction, the study will be stopped until the Data Safety Monitoring Board has time to convene and discuss the event and safety of the trial.

Given minimal adverse events with study drug and additional documentation from other larger clinical trials using oral itraconazole, the protocol was changed and approved such that hepatic function only needed to be checked at the beginning of the trial and monitored via symptoms and cardiac function was monitored with EKG and symptoms. As such, the DSMB with outside expertise on possible itraconazole adverse events seemed unnecessary. In its place, Drs. [name], [name] and [name] meet monthly to review all active trials and research projects associated with the rhinology group. At this meeting, any adverse events or irregularities with the trial will be reviewed and documented.

## Statistics

### Power analysis

This is a pilot study focused on estimating a range of plausible treatment effects. We anticipate enrolling **500 patients over a 3-4 year period** with an anticipated 15% dropout rate. A total of 340 subjects should

Table 2

Recurrence Rates		Power	Power
Placebo	Treatment	N=320	N=102
50%	20%	1.00	0.86
50%	25%	0.99	0.68
50%	30%	0.93	0.46
50%	35%	0.61	0.26

be available for final analyses. However, we also performed a power analysis should the number of possible patients be as low as 120 patients over the 3 years with similar 15% drop rate for possible N=102. Although the goal of this study is to estimate an unbiased treatment effect, we calculated power (Table 2) to detect a range of effect sizes (as reported in the literature) assuming a two-sided test with alpha of 0.05 and N=320 and 102. The study would have adequate power to detect a large effect size. The planned complementary Bayesian analyses will provide probabilities of clinically important treatment benefits to guide the conduct of future trials.

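### Table 2 gives power 0.61 for 50% versus 35% recurrence at N=320; the design has about 0.74 to 0.78, and the column's N of 320 disagrees with the 340 in the text

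*Combined protocol and SAP*

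**What the plan says.** The Power analysis section describes the trial as a pilot. It expects 500 patients over three to four years with 15% dropout, and then says "A total of 340 subjects should" be available for the final analyses. It adds a low-recruitment case of 120 patients, leaving 102 after the same dropout.

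Table 2 then gives power "assuming a two-sided test with alpha of 0.05 and N=320 and 102". Its rows (placebo rate, treatment rate, power at N=320, power at N=102) read:

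- "50% 20% 1.00 0.86"
- "50% 25% 0.99 0.68"
- "50% 30% 0.93 0.46"
- "50% 35% 0.61 0.26"

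Neither the test nor the software is named. Study Design (Aim 1) supplies the other two inputs: allocation is "1:1 ratio, stratified by presence of asthma", and 80% of up to 500 screened patients are expected to qualify, "allowing us to enroll about 400 CRSwNP patients undergoing sinus surgery".

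**The concern.** Within the N=320 column, power falls from 0.93 to 0.61 when the treatment rate moves from 30% to 35%. That drop looks too steep for 160 patients per arm. The column's N also differs from the number of analysable patients given in the same section.

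Table 2 is the plan's only statement of power, and this row is the smallest effect it shows. A reader who takes 0.61 at face value concludes that the trial has a 39% chance of missing a 15-point reduction in recurrence. The section also says that the trial's results are meant to guide later trials, so the figure may be carried forward.

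**Working it through.** **Inputs.** Two-sided alpha 0.05, total N of 320 and 102, and the recurrence rates come from the Power analysis section. The 1:1 ratio comes from Study Design, so n = 160 and n = 51 per arm.

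**Formula.** For two proportions with n per arm and pbar = (p1 + p2)/2:

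Power = Phi( ( |p1 − p2| − c − 1.96·sqrt(2·pbar·(1 − pbar)/n) ) / sqrt( (p1(1 − p1) + p2(1 − p2))/n ) )

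with c = 1/n for the continuity-corrected test and c = 0 for the uncorrected test.

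**Step 1: find the method from the N=102 column (n = 51).**

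| Rates | Stated | Corrected | Uncorrected |
|---|---|---|---|
| 50% v 20% | 0.86 | 0.856 | 0.900 |
| 50% v 25% | 0.68 | 0.677 | 0.749 |
| 50% v 30% | 0.46 | 0.459 | 0.541 |
| 50% v 35% | 0.26 | 0.263 | 0.333 |

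The corrected test matches all four entries; the uncorrected test matches none.

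**Step 2: apply both tests to the N=320 column (n = 160).** For 50% v 35%, pbar = 0.425:

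- 1.96·sqrt(2 × 0.425 × 0.575/160) = 0.1083
- sqrt((0.25 + 0.2275)/160) = 0.0546
- Corrected: (0.15 − 0.00625 − 0.1083)/0.0546 = 0.648, so power is 0.742
- Uncorrected: (0.15 − 0.1083)/0.0546 = 0.763, so power is 0.777

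| Rates | Stated | Corrected | Uncorrected |
|---|---|---|---|
| 50% v 20% | 1.00 | 0.9999 | 0.9999 |
| 50% v 25% | 0.99 | 0.996 | 0.997 |
| 50% v 30% | 0.93 | 0.946 | 0.958 |
| 50% v 35% | 0.61 | 0.742 | 0.777 |

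Under the corrected test the first entry is right and the next two are low by less than 2 points. The last is low by 13 points, or 17 against the uncorrected value.

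**Step 3: try other methods for that cell at N=320.** The unpooled normal approximation gives 0.784 and the arcsine method 0.778. Exact enumeration gives 0.773 for Pearson chi-square and 0.738 for both Yates and Fisher. The full range is 0.738 to 0.784. A one-sided 0.05 test moves further away (0.833, corrected), and even 3:1 allocation gives 0.66 (uncorrected).

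**Step 4: try other sample sizes (corrected test).** The total N that rounds to each stated entry is:

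- 0.99 (50% v 25%): 264 to 312
- 0.93 (50% v 30%): 294 to 304
- 0.61 (50% v 35%): 242 to 244

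The first three entries of the column fit jointly at N = 294 to 304, where 50% v 35% has power 0.70 to 0.72. At N = 242 to 244, 50% v 30% would have power 0.87, not 0.93. No single N yields the column.

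**Step 5: trace the analysis N.**

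- 500 × 0.80 = 400 enrolled (Study Design)
- 400 × 0.85 = 340 (Power analysis text)
- 120 × 0.85 = 102 (low-recruitment case, consistent)
- 320 is not derived anywhere; from 400 it would need 400 × 0.80, that is, 20% dropout

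At N=340 (n = 170), power for 50% v 35% is 0.769 corrected and 0.802 uncorrected.

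**The case against.** The best reply is that 0.74 is inferred, because the plan names no test and its N is itself in dispute. That is fair, and 0.74 should be read as conditional on the test that the N=102 column reveals and on N=320. It does not rescue 0.61, since every two-sided 1:1 method tried at N=320 gives at least 0.738.

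A second point concerns the cause. With the corrected test, N=300 gives 1.00, 0.99, 0.93 and 0.71, so a column computed at 300 with one digit mistyped would explain all four entries. This is plausible, but 300 appears nowhere in the plan and the cause cannot be established from the documents. On that account both the cell and the column's N would still be wrong.

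A third point is that the consequence is small. This stands. The trial is a pilot aimed at estimation, the error understates power, nothing in the design depends on it, and at N=320 the row stays below 0.80 by every two-sided 1:1 method. Only at N=340 without the correction does it just reach 0.80.

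Finally, the N problem is wider than 320 against 340. The Power analysis section speaks of enrolling 500, which with 15% dropout would leave 500 × 0.85 = 425, whereas Study Design has 500 screened and about 400 enrolled. That adds to the inconsistency and belongs in the same correction.

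**Conclusion.** The concern holds. The 0.61 is wrong under every method tried for a two-sided 0.05 test with equal arms. The value at N=320 is 0.74 if the table used the continuity-corrected test, as its N=102 column indicates, and 0.78 if it did not. The chance of missing a 15-point reduction is therefore 26% or 22%, not 39%. Separately, the table's N=320 conflicts with the 340 that follows from the plan's own enrolment and dropout figures.

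The statement that power is adequate for a large effect remains true. The matter should be corrected because the figure is certainly wrong and cheap to put right, although its consequences are modest.

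**What to change.** 1. Name the test behind Table 2.
2. Choose one analysis N, state the dropout rate that produces it, and align the table, the text and the enrolled-versus-screened figures (500, 400, 340, 320).
3. Recompute the column on that N.

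| Test, N | 50% v 20% | 50% v 25% | 50% v 30% | 50% v 35% |
|---|---|---|---|---|
| Corrected, 320 | 1.00 | >0.99 | 0.95 | 0.74 |
| Corrected, 340 | 1.00 | >0.99 | 0.96 | 0.77 |
| Uncorrected, 320 | 1.00 | >0.99 | 0.96 | 0.78 |
| Uncorrected, 340 | 1.00 | >0.99 | 0.97 | 0.80 |

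With the corrected test the N=102 column stays as printed. If an uncorrected test is intended, that column must change too, to 0.90, 0.75, 0.54 and 0.33.

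The cost is one table column (two if the uncorrected test is chosen), its heading, the name of the test and a few words on sample numbers. The design and the sentence on large effects do not change.
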